## 10.2. Secondary Efficacy Outcomes

The key secondary endpoints are:

- Change from Baseline in BC-CCI overall score to the end of each treatment period for solriamfetol versus placebo
- Change from Baseline in PGI-S to the end of each treatment period for solriamfetol versus placebo
- Percent of participants with an at least 1 category improvement in the PGI-S from Baseline to the end of each treatment period for solriamfetol versus placebo
- Percent of participants with an at least 1 category improvement in the BC-CCI from Baseline to the end of each treatment period for solriamfetol versus placebo
- Change from Baseline in ESS score to the end of each treatment period to the end of each treatment period for solriamfetol versus placebo
- Change in DSST RBANS score at 2 hours postdose from Baseline to the end of each treatment period for solriamfetol versus placebo
- Change in DSST RBANS score at 4 hours postdose from Baseline to the end of each treatment period for solriamfetol versus placebo
- Change in DSST RBANS score at 6 hours postdose from Baseline to the end of each treatment period for solriamfetol versus placebo
- Change in DSST RBANS score at 8 hours postdose from Baseline to the end of each treatment period for solriamfetol versus placebo

The variables related to change from baseline will be analyzed using the same methods used to analyze the primary efficacy variable.

Variables related to percentages will be analyzed via exact methods. Percentages of responders for the two treatments will be presented. The percentages, percentage differences, and the two-sided 95% confidence intervals of the differences as well as the p-values of the differences will be presented.

In these analyses, missing values will be considered failure.

## 10.3. Exploratory Endpoint(s)

[figure not shown]
The exploratory endpoints are the correlations between the change from Baseline at the end of each double-blind study treatment period in ESS and DSST RBANS score, BC-CCI, and PGI-S. Nominal p values will be provided with appropriate 95% CIs for the exploratory endpoints.

## 10.4. Missing Value Handling Procedures

Unless otherwise stated, missing values will not be imputed.

## 10.5. Interim Analyses

No interim analysis will be performed.

## 10.7. Power and Sample Size Justification

The new Sponsor has determined to conclude the study. The sample size justification provided by the protocol prior to the Amendment is outlined below:

A sample size of 49 participants per treatment sequence for a total sample size of 98 will provide 90% power to detect a difference of 3 points in means for the change from Baseline to Week 2 on DSST RBANS scores between solriamfetol and placebo, assuming a standard deviation of 9 points in the change in DSST (the cross over analysis of variance [ANOVA] root mean squared error (RMSE) is 6.36). The sample size estimates are based on the results from Trintellix randomized parallel placebo-controlled trials ([McIntyre 2014](#); [Mahableshwarkar 2015](#)). The change from Baseline to Week 8 resulted in an estimated delta on DSST performance score of 1.8 ~ 4.3 (average 3.4) and SD of 6.6 ~ 8.6. Another reference is a crossover study with 5 dosages of MK-0249, modafinil 200 mg, and placebo and each period is 2 weeks, the RMSEs are estimated from 4.4 ~ 5.7 ([Herring 2013](#)). It is increased to 6.36 to account for uncertainty in sample size assumptions. A 1-sided significance level of 0.025 using a 2 group t-test (crossover ANOVA) is used in the sample size calculation. Assuming a correlation of 0.5 between periods

on DSST, a delta of 3, a standard deviation of 9, and a 15% dropout rate, a total of 116 (58 participants per treatment sequence) will be randomized.

## 11. SAFETY ANALYSES

Safety analyses will be performed on the Safety Population. Safety evaluations will be based on the incidence and severity of adverse events, as well as on ECG measurements, vital signs and Columbia Suicide Severity Rating Scale (C-SSRS). Safety variables will be tabulated and presented by study drug actually received.

In this crossover study, AEs will be attributed to the last treatment the participant received prior to the AEs.

Because there is no pre-specified safety outcome defined in terms of AEs or vital signs, any formal comparisons between the treatment arms with respect to specific safety parameters will be post-hoc.

### 11.1. Extent of Exposure

Summary statistics of exposure to study drug will be tabulated by treatment group. The exposure is defined as last dosing date – first dosing date + 1. The exposure will be summarized by summary statistics as well as by weekly frequency. Compliance is calculated as follows: compliance rate (%) = (number of tablets expected to be taken – number of missed doses /number of tablets should have been taken)\*100.

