4.1.3. Double-blind Treatment Period (Treatment Period 1)

Throughout this protocol, the Double-blind Treatment Period will be referred to as Treatment Period 1. Treatment Period 1 begins the day after the Baseline and Randomization visit. Participants will take the first dose of study intervention at home upon waking the first day of the period. Participants will take study intervention at home until the next visit, but will be instructed by site staff to not take the final dose until after arrival at the study site, and to bring pill bottle/blister pack of study intervention to the site.

The last day of Treatment Period 1 is a site visit. Participants will turn in pill bottle/blister pack, take the final dose of study intervention for that treatment period in the presence of site staff, and undergo the assessments outlined in [Section 1.3](#). At the end of the study site visit, participants will be provided with a supply of double-blind crossover study intervention for Treatment Period 2, but will be instructed to not to take any doses until after the 1-week washout. Site staff will then schedule the next visit to occur after the 1-week washout and 2-week double-blind crossover treatment periods are completed.

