8.1.6. Timing of Study Intervention Dosing

Participants should take the study intervention dose once daily upon awakening (except for site visit days) and avoid administration within 9 hours of planned bedtime because of the potential to interfere with sleep. If the subject cannot take the study drug at least 9 hours before his/her anticipated bedtime, the subject should not take the study drug for that day.

For site visits, participants should not take their daily dose upon awakening. Instead, they should arrive at the study site 30 minutes prior to the time of drug administration (eg, 8:30 AM) for assessments so that they can take study intervention under site supervision promptly as scheduled (eg, 9:00 AM).

After the first Treatment Period 1 visit, participants will undergo a 1-week washout, where participants will not take any study intervention during this time.

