### 4.3.1. Summary

This is a phase 4, multicenter, randomized, double-blind, placebo-controlled, crossover study comparing solriamfetol 150 mg to placebo on tests of cognitive function in participants with EDS due to OSA. Participants will be in the study for approximately 8 weeks, including 2 weeks of solriamfetol treatment and 2 weeks of placebo treatment. Each participant will receive both double-blind treatment conditions, but will be randomized to undergo the conditions in a different sequence.

Cognitive function in this study will be assessed by the DSST RBANS (an objective test) and the British Columbia Cognitive Complaints Inventory (BC-CCI) (a subjective test). The DSST RBANS has been used for decades to measure cognitive function. The BC-CCI was developed to measure cognitive complaints in individuals with major depressive disorder (MDD) and has also been used to measure cognitive deficits in individuals with poor sleep quality.

The primary endpoint is the change from the average of the DSST RBANS scores at Baseline to the average of the postdose (2-, 4-, 6-, and 8-hours) DSST RBANS scores at the end of each double-blind treatment period. The secondary endpoints include: the change in overall score and categorical change from Baseline at the end of each double blind treatment period in BC-CCI; the change from each of the 2-, 4-, 6-, and 8 hour DSST RBANS scores at Baseline to each of the corresponding 2-, 4-, 6-, and 8-hour postdose DSST RBANS scores at the end of each double blind treatment period; change in overall score and categorical change from Baseline at the end of each double-blind treatment period in PGI-S; and change in overall score from Baseline to the end of each double-blind treatment period in ESS.

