### 6.5. Per Protocol Population

The Per Protocol population will include all mITT participants without important major protocol violations. The criteria for important major protocol violation will be determined and documented prior to database lock and unblinding of treatment codes. Participants with important major protocol violations will be flagged in data listings.

Additional efficacy analyses may be performed on the Per Protocol population.

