## **12. IDENTIFICATION AND SUMMARY OF PROTOCOL DEVIATIONS**

Important major protocol deviations, such as entry criteria violation and significant treatment non-compliance will be summarized as far as they can be extracted from numeric or coded study data.

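### The compliance rate in SAP 11.1 divides only the missed doses, so it overstates compliance by 100(E − 1) percentage points, where E is the number of doses expected

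*SAP*

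**What the plan says.** SAP 11.1 (Extent of Exposure) gives the compliance rate as a percentage. The content of its only bracket is "number of tablets expected to be taken – number of missed doses /number of tablets should have been taken", and the bracket is then multiplied by 100. There is no inner bracket around the subtraction, so the division belongs to the last part alone: "number of missed doses /number of tablets should have been taken".

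No other section gives a formula, a worked example or a numerical cut-off. Protocol 6.4 has sites check compliance at each visit and record departures from the regimen, without saying how a rate is calculated.

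Two other SAP sections touch on compliance or on the violations it may feed:

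- SAP 12, on important major deviations, says that "entry criteria violation and significant treatment non-compliance will be summarized". It does not define the term numerically or refer to 11.1.
- SAP 6.5 says "The Per Protocol population will include all mITT participants without important major protocol violations". The criteria are to be settled before database lock and unblinding, and compliance is not mentioned.

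**The concern.** This is an operative derivation rule, not background text. By ordinary operator order the division binds to the missed doses alone, so the rule returns roughly 100 times the number of doses expected, less a small term for the doses missed.

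SAP 3 says the approved plan governs the analyses for the Clinical Study Report and that departures from it will be noted there. A programmer who follows the text produces impossible percentages. One who silently inserts the missing bracket departs from the approved plan without a record.

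At stake is the compliance summary in the exposure section, and any non-compliance flag that is later built on the same variable.

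**Working it through.** **Inputs**

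- E, doses expected in a period. The documents state no count. SAP 4.3.1 describes participation as "including 2 weeks of solriamfetol treatment and 2 weeks of placebo treatment", and Protocol 8.1.6 says "Participants should take the study intervention dose once daily upon awakening". That gives a nominal E = 14, which is an assumption.
- Range of E in Period 1. Protocol 4.1.3 says "Treatment Period 1 begins the day after the Baseline and Randomization visit". With randomization on Day 0, the first dose is on Day 1. The last dose is taken at Visit 5, on Day 13 to 16 in the Schedule of Assessments. So E runs from 13 to 16.
- M, doses missed. Missed days are foreseen: where a dose cannot be taken early enough before bedtime, Protocol 8.1.6 says "the subject should not take the study drug for that day".
- The SAP uses two phrases for the number of tablets due, one before the minus sign and one after the slash. Nothing distinguishes them, so both are taken as E.

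**Formulas**

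- As printed: (E − M/E) × 100 = 100E − 100M/E
- As evidently intended: (E − M)/E × 100 = 100 − 100M/E
- Difference: 100E − 100 = 100(E − 1) percentage points, whatever M is. At E = 14 this is 1,300 points.

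The documents report no compliance figure, so there is none to reproduce.

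**Results**

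| E | M | As printed | As intended |
|---|---|---|---|
| 13 | 0 | 1300.0% | 100.0% |
| 13 | 2 | 1284.6% | 84.6% |
| 14 | 0 | 1400.0% | 100.0% |
| 14 | 1 | 1392.9% | 92.9% |
| 14 | 2 | 1385.7% | 85.7% |
| 14 | 7 | 1350.0% | 50.0% |
| 14 | 14 | 1300.0% | 0.0% |
| 16 | 1 | 1593.75% | 93.75% |

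For example, (14 − 1/14) × 100 = 1392.9, against (14 − 1)/14 × 100 = 92.9.

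**What the results show**

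1. For one or two missed doses and E = 13 to 16, the printed rule gives about 1,285% (E = 13, M = 2) to 1,594% (E = 16, M = 1).
2. At a fixed E, each missed dose lowers both versions by the same 100/E points, which is 7.1 at E = 14. Rank order is kept.
3. Across different E, comparability is lost. Full compliance at E = 13 gives 1300.0%, the same value as no doses taken at E = 14. One extra scheduled day adds 100 points when no dose is missed, far more than the 7.1 points lost with a missed dose.
4. The lowest value the printed rule can return is at M = E, namely 100(E − 1). At E = 13 this is 1,200%. No cut-off at or below 100% could separate compliant from non-compliant participants.

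**The case against.** The best reply is that the intent is obvious. The quantity is labelled a percentage rate, the sentence reads naturally as expected minus missed over what was due, and a table showing about 1,390% would be noticed at first output. This stands as a reason to call the error minor. It does not make the rule right, since the plan is meant to be followed as approved and no other section supplies the correct form.

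Three stronger readings are tempting, and the documents do not support them.

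- A reader might infer that the printed value hardly responds to missed doses. In percentage points it falls exactly as fast as the correct rate. It changes little only in relative terms: at E = 14, one missed dose moves it by about 0.5% of its value (7.1/1400), against 7.1% for the correct rate.
- A reader might infer that non-compliance could not be found at all. At a fixed E the ranking is intact. Sites also check compliance and record regimen deviations independently of this formula (Protocol 6.4), and non-compliance is a listed reason for stopping study intervention (Protocol 7.1).
- A reader might infer that the Per Protocol set will wrongly keep non-compliant participants. SAP 6.5 and SAP 12 neither cite the 11.1 formula nor set a threshold, and the violation criteria are still to be fixed. Per Protocol efficacy analyses are themselves optional. The link exists only if the sponsor chooses to make it.

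**Conclusion.** The formula is wrong as written, and the error is minor. It overstates compliance by 100(E − 1) percentage points: 1,300 points at the assumed E = 14, and 1,200 to 1,500 points over E = 13 to 16. The result is not a percentage, cannot be judged against any cut-off of 100% or less, and mixes visit timing with adherence when participants have different E.

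The direct effect is confined to the descriptive compliance summary. An effect on deviation reporting or the Per Protocol set is conditional on those flags being derived from this variable. The primary analysis is unaffected, because membership of the mITT population (SAP 6.4) does not depend on compliance.

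The conclusion rests on reading the printed expression by standard operator order and on treating the two terms for doses due as the same number. The direction and form of the error do not depend on E = 14; only the illustrative figures do.

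**What to change.** Replace the sentence in SAP 11.1 with:

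Compliance (%) = [(number of doses expected − number of doses missed) / number of doses expected] × 100, calculated separately for each treatment period.

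Use one term for the denominator and one unit (doses); the present wording mixes tablets with doses and has two names for the number due. State that the expected number is counted from the participant's actual dosing days in that period, since the visit window lets it vary.

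If the sponsor intends to use this rate for the non-compliance deviation in SAP 12 or for Per Protocol membership, the SAP should say so and give the numerical criterion before database lock.

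The cost is one line of SAP wording, plus one more if the rate is to feed a flag. No data collection or primary analysis changes.

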### 11.2. Adverse Events

Each AE and SAE term will be recorded as a verbatim term on the case report forms (CRFs). All AEs and SAEs will be coded by primary System Organ Class (SOC) and mapped to a preferred term using the MedDRA Version 24.0. The investigator will assess AE severity and relationship to the study treatment.

All AEs will be listed. However, only treatment emergent adverse events (TEAEs) will be included in the AE summaries. A TEAE is defined as any AE with an onset date in the interval between the first study treatment dosing date and 7 days after the last study treatment dosing date. In addition, any AEs that the investigators deem to be treatment related will also be considered TEAEs and will be included in the AE summaries.

For the purpose of calculating treatment emergence and inclusion in summary tables, incomplete onset dates will be imputed using the method described in Appendix A.

AEs will be summarized by the number and percentage of participants in each primary SOC and preferred term. Participants will be counted only once for each primary SOC and each preferred term. Summary tables of AEs by primary SOC, preferred term and severity will be provided. If a participant has more than one AE coded to the same preferred term, the participant will be counted only once for that preferred term by using the event with the highest severity. Similarly, if a participant has more than one AE within a primary SOC category, the participant will be counted only once in that SOC category by using the event with the highest severity. AEs by

primary SOC, preferred term and relationship to study drug will be provided as well. If a participant has more than one AE coded to the same preferred term, the participant will be counted only once for that preferred term by using the most related event. Similarly, if a participant has more than one AE within a primary SOC category, the participant will be counted only once in that primary SOC category by using the most related event. In addition, serious adverse events (SAEs) by primary SOC and preferred term will be provided. Deaths and SAEs will be summarized similarly to AEs. All adverse event tables will also include the total number of events, counting multiple events per participant.

In the AE summary, preferred terms within each SOC will appear in descending frequency order within each active treatment group.

Frequencies for deaths and hospitalizations will also be summarized by treatment group and overall.

Columbia–Suicide Severity Rating Scale (C-SSRS) data will be summarized at scheduled visits and will be listed.

Other safety analyses will be performed as appropriate.

### **11.3. Clinical Laboratory Tests**

Clinical laboratory tests including hematology, serum chemistry, urinalysis, and thyroid panel, will be collected at Screening only. The results will be presented in the listings.

### **11.4. ECG**

Electrocardiograms (ECG) will be collected at screening only. ECG results will be presented in a listing.

### **11.5. Vital Signs**

Vital sign values and change from baseline in the vital signs will be summarized by treatment that the participants last received.

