2.3. Benefit/Risk Assessment

2.3.1. Risk Assessment

Solriamfetol has a robust clinical safety database comprised of healthy adult participants and participants with OSA, narcolepsy, Parkinson's disease, and MDD with a consistent safety profile across conditions. Solriamfetol is approved in the US for the indication of improving wakefulness in adult patients with EDS associated with OSA or narcolepsy. Solriamfetol is approved in the EU for the indication of improving wakefulness and for reducing EDS in adults with narcolepsy (with or without cataplexy) or OSA, whose EDS has not been satisfactorily treated by primary OSA therapy. The risks to participants in this study are expected to be similar to those seen in prior clinical studies that evaluated the effects of 75 mg and 150 mg solriamfetol in OSA and narcolepsy participants, including those on concomitant antidepressants. Current information on the efficacy, pharmacokinetics (PK), and safety of solriamfetol is provided in the solriamfetol Investigator's Brochure (IB), the United States Package Insert (USPI) and the Summary of Product Characteristics (SmPC).

Underlying psychiatric comorbidities (ie, affective disorders and suicidal ideation), commonly seen in OSA and narcolepsy patients, could be exacerbated by the use of a stimulant or wake-promoting agent. In the solriamfetol clinical development program, serious psychiatric events occurred more commonly in the narcolepsy population than the OSA population. Further, although solriamfetol blocks dopamine and norepinephrine reuptake, nonclinical and clinical data show that the potential for abuse for solriamfetol is low.

Transient and dose-dependent increases in blood pressure (BP) and heart rate (HR) have been seen in clinical studies with OSA and narcolepsy participants. This population may be at risk for cardiovascular events due to certain intrinsic factors, such as increasing age, obesity, concurrent diabetes mellitus or cardiovascular disease, hyperlipidemia, and hypertension. In addition, the underlying disease pathophysiology may also predispose patients to cardiovascular disease. Based on the cardiovascular comorbidities in this population and depending on the cardiovascular risk profile, these events are anticipated to occur in this population.

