4.2. Scientific Rationale for Study Design

A randomized, double-blind, placebo-controlled crossover study design has been selected for this study as it allows for an intra-participant comparison between solriamfetol and placebo in evaluating cognitive function. The crossover study design is appropriate in this study as the cognitive impairment and EDS associated with OSA are chronic and stable conditions, and the

treatment would not result in total cure but only alleviate the condition. This design also reduces the overall number of participants exposed to the test hypothesis required for evaluation.

Two-week treatment for each period is selected for the following reasons:

- Solriamfetol has a half-life of approximately 7 hours.
- Once daily solriamfetol dose of 150 mg reaches steady state within 3 days.
- Pivotal studies evaluating solriamfetol demonstrated that the effect of solriamfetol was seen as early as after 1-week treatment.

A 1-week washout period between the 2 double-blind treatment periods will minimize any potential carryover effect.

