15. Presence of significant cardiovascular disease including but not limited to: myocardial infarction within the past year, unstable angina pectoris, symptomatic congestive heart failure (ACC/American Heart Association stage C or D), revascularization procedures within the past year, uncontrolled atrial fibrillation, ventricular cardiac arrhythmias requiring automatic implantable cardioverter defibrillator or medication therapy, uncontrolled hypertension (as defined by Centers for Disease Control and Prevention), systolic blood pressure ≥ 155 mmHg or diastolic blood pressure ≥ 95 mmHg (at Screening

or Baseline), or any history of cardiovascular disease or any significant cardiovascular condition that in the investigator's opinion may jeopardize participant safety in the study.

16. Laboratory value(s) outside the laboratory reference range that is considered to be clinically significant by the investigator (clinical chemistry, hematology, and urinalysis).
NOTE: Screening labs may be repeated once.
17. Hypothyroidism or hyperthyroidism, unless stabilized by appropriate medication for at least 3 months prior to Screening (a normal thyroid-stimulating hormone is required prior to Randomization at Baseline).

Prior/Concomitant Therapy

18. Use of any over-the-counter (OTC) or prescription medications that could affect the evaluation of EDS within a time period prior to the Baseline visit corresponding to at least 5 half-lives of the drug(s) or planned use of such drug(s) at some point throughout the duration of the 5-week double-blind treatment period. Examples of excluded medications include OTC sleep aids, stimulants (eg methylphenidate, amphetamines, modafinil, and armodafinil), sodium oxybate, pemoline, pitolisant, bupropion, trazodone, vortioxetine, duloxetine, tricyclic antidepressants, hypnotics, benzodiazepines, pseudoephedrine, barbiturates, and opioids. Medications should be discontinued such that, in the opinion of the investigator, the participant has returned to his/her Baseline level of daytime sleepiness at least 7 days prior to the Baseline visit.
19. Current or recent (within the past 2 years) diagnosis of a moderate or severe substance use disorder (excluding caffeine) according to DSM-5 criteria, or seeking treatment for a substance-related disorder. Nicotine use disorder is excluded only if it has an effect on sleep (ie, a participant who routinely awakens at night to smoke).

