8.4.2. Vital Signs

Vital signs will be collected prior to study intervention administration for Visit 5 and Visit 8.

- Oral temperature, pulse rate, respiratory rate, and BP will be assessed.

- Blood pressure and pulse measurements will be assessed in the sitting position with a completely automated device. Manual techniques will be used only if an automated device is not available.
- Blood pressure and pulse measurements should be preceded by at least 5 minutes of rest for the participant in a quiet setting without distractions (eg, television, cell phones).
- Vital signs (to be taken before blood collection for laboratory tests) will consist of 1 pulse and 3 BP measurements (3 consecutive BP readings will be recorded at intervals of at least 1 minute). The average of the 3 BP readings will be recorded.
- For clinically significant abnormal vital signs results, sites should document them in the medical history (Screening and Randomization) or as AEs (after initiating study intervention).

8.4.3. *Electrocardiograms*

- Single 12-lead ECG will be obtained as outlined in the SoA (see [Section 1.3](#)) using an ECG machine that automatically calculates the HR and measures PR, QRS, QT, and corrected QT interval (QTc) intervals. Any abnormal safety assessments including ECG readings considered clinically significant in the medical and scientific judgment of the investigator should be reported as an AE ([Appendix 4](#)). The investigator should review the ECG and document that review in the source documents.
- For clinically significant abnormal ECG results, sites should document them in the medical history (Screening results) or as AEs (after initiating study intervention).

8.4.4. *Clinical Safety Laboratory Assessments*

- See [Appendix 3](#) for the list of clinical laboratory tests to be performed and to the SoA ([Section 1.3](#)) for the timing and frequency.
- The investigator must review the laboratory report, document this review, and record any clinically significant changes occurring during the study as an AE (after initiation study intervention). The laboratory reports must be filed with the source documents.
- Abnormal laboratory findings associated with the underlying disease are not considered clinically significant unless judged by the investigator to be more severe than expected for the participant's condition.

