### 7.1. Definition of Baseline

Unless otherwise stated, the last observed measurement prior to or on the date of randomization will be considered the baseline measurement. For the primary endpoint, baseline for the DSST RBANS will be the average of the 4 DSST RBANS scores (2-, 4-, 6-, and 8 hour) at Visit 3.

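### SAP 11.5 plans no within-participant solriamfetol-minus-placebo contrast for blood pressure and pulse, so the display of a named risk gives up the crossover's precision

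*SAP*

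**What the plan says.** Protocol 2.3.1 names the risk: "Transient and dose-dependent increases in blood pressure (BP) and heart rate (HR) have been seen in clinical studies with OSA and narcolepsy participants". Vital signs are one of three safety and tolerability measures in the objectives tables of both documents.

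The analysis is in SAP 11.5: "Vital sign values and change from baseline in the vital signs will be summarized by treatment that the participants last received". SAP 7 supplies the statistics (n, mean, SD, median, minimum, maximum). SAP 7.1 sets one baseline for both periods: "the last observed measurement prior to or on the date of randomization will be considered the baseline measurement", which for vital signs is normally Visit 3.

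On measurement, Protocol 8.4.2 says "Vital signs will be collected prior to study intervention administration for Visit 5 and Visit 8" and "The average of the 3 BP readings will be recorded". The schedules of assessments list vital signs at Visits 1, 3, 5 and 8, and none at Visit 9 (safety follow-up or early discontinuation).

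On inference, Protocol 9.4.5 plans no formal safety testing, and SAP 11 adds that "any formal comparisons between the treatment arms with respect to specific safety parameters will be post-hoc". Protocol 5.2 (criterion 15) excludes anyone at or above 155 mmHg systolic or 95 mmHg diastolic at Screening or Baseline. It sets no numeric pulse limit.

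**The concern.** In a crossover the informative quantity for a continuous safety measure is each participant's own solriamfetol-minus-placebo difference. Protocol 4.2 chose the design because "it allows for an intra-participant comparison between solriamfetol and placebo". That sentence goes on to speak of cognitive function, but the same participants give blood pressure and pulse under both treatments, so the same comparison is available at no extra cost.

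SAP 11.5 stops at two treatment columns. Without the within-participant correlation, nobody can recover the standard error of the difference from those columns. A modest real effect on a known risk would then look less certain than the data make it. Because formal comparisons are left post hoc, an estimate produced later would not have been specified in advance.

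Two smaller gaps follow. Anyone who leaves after Visit 5 and before Visit 8 is in one column only. And a mean, SD and maximum do not show how many participants reach the level that the protocol treats as too high for entry.

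**Working it through.** **The plan's own figure.** The documents give no precision figure for vital signs. The sample size for the primary endpoint shows how much the design relies on pairing:

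- Inputs (Protocol 9.2): SD of change 9, correlation 0.5, difference 3, one-sided 0.025, 98 completers, 15% dropout.
- RMSE = 9 × √(1 − 0.5) = 6.36, as stated. SD of the within-participant difference = 6.36 × √2 = 9.
- Noncentral t power is 0.904 at 98 participants, and 98 / 0.85 = 115.3, rounded up to 116. Both stated sizes reproduce.
- Standard error, paired: 9 / √98 = 0.91. From two columns read as independent: 9 × √(2/98) = 1.29. Ratio 1.41.

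**The same check for vital signs.** Let n be the number of completers, s the SD of change, and c the correlation between a participant's two changes.

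- Half-width from two columns read as independent: 1.96 × s × √(2/n)
- Half-width, paired: 1.96 × s × √(2(1 − c)/n)
- Ratio: 1 / √(1 − c), whatever s and n are

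Both changes share one baseline. If b is the correlation of baseline with each period's reading and p the correlation between periods, with equal SDs at all visits, then c = (1 − 2b + p) / (2(1 − b)).

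- b = p (equal correlations): c = 0.5, ratio 1.41. The paired interval is 1 − 1/1.41 = 29% narrower.
- b = 0.7, p = 0.5: c = 0.17, ratio 1.10 (9% narrower).
- b = 0.5, p = 0.8: c = 0.80, ratio 2.24 (55% narrower).

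Half-widths with n = 98 and c = 0.5, for **assumed** SDs of change:

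- 10 mmHg: 2.80 from two columns, 1.98 paired
- 12 mmHg: 3.36 and 2.38
- 14 mmHg: 3.92 and 2.77

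Starting instead from an assumed SD of 10 to 15 mmHg for a single visit's value and an equal correlation of 0.5 to 0.8, the ranges are 1.77 to 4.20 mmHg from two change columns and 1.25 to 2.97 mmHg paired. The value columns do not help: read as independent, their ratio is 1 / √(1 − p), which is 1.41 to 2.24 for p from 0.5 to 0.8.

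**Unmatched columns.** The plan allows for 116 − 98 = 18 participants lost. As an upper illustration, if all 18 left after Visit 5, split evenly between sequences, each column would hold 98 + 9 = 107 people, of whom 98 are common to both. Those who leave before Visit 5 have no scheduled on-treatment reading and are in neither column. Protocol 6.5 and 7.1.1 discontinue participants who do not tolerate solriamfetol, so leaving may depend on treatment.

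**The case against.** The strongest case is that descriptive safety reporting is a stated choice, and that the material is largely covered elsewhere. Protocol 8.4.2 sends clinically significant abnormal vital signs to the adverse event record, which SAP 11.2 tabulates. SAP 7 gives the maximum and lists all CRF data by participant, so pairs could be rebuilt. SAP 11.2 also allows other safety analyses as appropriate. The plan computes no interval from the two columns, so the wide interval is one a reader would construct.

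Much of this stands as fact, but none of it supplies the estimate. Adverse event recording depends on investigator judgement, listings are not a summary, and an open clause specifies nothing. An estimate with an interval is not a test, so it can sit beside Protocol 9.4.5 and SAP 11 if labelled as descriptive.

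The 155/95 limit is an entry criterion, and the documents do not use it as an on-treatment harm threshold. That objection stands, so the count is only a supplement. Under assumed means of 120 to 135 systolic and 76 to 84 diastolic, SDs of 12 to 15 and 8 to 10, and visit correlations of 0.5 to 0.8, simulation puts about 0.1 to 5.6% of eligible participants at or above the systolic limit on placebo, and 0.4 to 6.7% at or above the diastolic limit. A case is new since entry, but not thereby drug-related, and the count must be read against placebo.

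A reader might also infer that the entry limit biases the comparison, because baseline is cut off from above and later readings drift up. The documents do not support that. SAP 11.5 summarises values as well as changes, and the values carry no such baseline shift. Under the same assumptions the drift in a change column is about 0 to +1.1 mmHg systolic and 0 to +0.8 diastolic. It is equal under both treatments, visible in the placebo column, and cancels for participants with both periods (simulated difference 1.98 to 2.02 for a true 2.00). Pulse has no entry limit.

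**Conclusion.** The point holds as one of lost precision and unmatched columns. SAP 11.5 leaves out the contrast that the crossover makes available for a named risk. Reading the two change columns as independent inflates the interval by about 1.41 under equal visit correlations, and by 1.10 to 2.24 over the correlations examined. The factor does not depend on the SD or on n. The mmHg figures rest on assumed SDs and on 98 completers, and SAP 10.7 says the new sponsor has determined to conclude the study, so n may be smaller and every interval wider.

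It would go too far to conclude that the plan hides a harm or reports a biased effect. The documents give no effect size for blood pressure from which to say how many participants would be affected. The Visit 5 and Visit 8 readings also precede that day's dose. With the stated half-life of about 7 hours, roughly 0.5^(24/7) = 9% of the previous day's dose remains 24 hours later. A better analysis of these readings cannot show what happens soon after dosing. This is a cheap improvement that should be made, not a defect that threatens the trial's conclusions.

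**What to change.** Keep the planned summaries and add to SAP 11.5:

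1. For systolic pressure, diastolic pressure and pulse, the within-participant solriamfetol-minus-placebo difference at the end-of-period visits, adjusted for period, with a two-sided 95% CI. With complete pairs this is the equally weighted average of the two sequence-specific mean differences. The shared baseline cancels. Label it a descriptive estimate with no test and no p-value, and state that it is not a formal comparison in the sense of SAP 11. Show the number of pairs beside the number in each column.
2. As a descriptive supplement, the number and percentage by treatment at or above 155 mmHg systolic or 95 mmHg diastolic at Visits 5 and 8, using the recorded average of the three readings. The denominator is the participants with a reading on that treatment. State that the level is the protocol's entry limit, used for reporting only and not as a management rule.

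The cost is SAP wording before database lock and a few table rows from data already collected. The paired estimate rests mainly on participants with both periods, which is why the planned columns should stay. The pre-dose timing is untouched and should be stated as a limit when the results are read.
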